**The University of Texas Southwestern Medical Center at Dallas
Institutional Review Board**

Protocol

Title: Brexpiprazole for Bipolar Disorder

Principal Investigator: E. [name]., Ph.D.

Funding Sponsor: Otsuka America Pharmaceuticals, Inc.

1. Introduction and Purpose:

Brexipiprazole is effective for both major depressive disorder and schizophrenia. However, to date no studies have examined its safety and efficacy in bipolar disorder. We hypothesize that brexpiprazole will be associated with a reduction in depressive symptom severity in outpatients with bipolar disorder, depressed mood state. The proposed open-label trial will examine brexpiprazole in a group of 20 bipolar depressed outpatients.

Primary Aim: Determine if brexpiprazole is associated with a reduction in depressive symptom severity using The Montgomery-Asberg Depression Rating Scale (MADRS) in outpatients with bipolar disorder, depressed mood state.

Secondary Aims:

- 1) Assess manic symptoms in patients with bipolar disorder receiving brexpiprazole.
- 2) Assess cognition in patients with bipolar disorder receiving brexpiprazole.
- 3) Assess the safety and tolerability of brexpiprazole in patients with bipolar disorder.
- 4) Assess quality of life in patients with bipolar disorder receiving brexpiprazole.

Additional Exploratory Analyses:

- 1) Assess peripheral inflammation in patients with bipolar disorder receiving brexpiprazole.
- 2) Assess relationships between changes in outcome measures.

2. Background:

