For Baseline 2 (~2 hours), recent depressive symptoms will be assessed via the IDS-SR₃₀ and MADRS, mania via the YMRS, current mood via Internal State Scale (ISS), suicidal ideation will be assessed via the Columbia Suicide Severity Rating Scale (CSSRS), safety and side effects will be assessed with the SAFTEE, the Abnormal Involuntary Movement Scale (AIMS), Barnes Akathisia Scale (BAS) and Simpson-Angus Scale (SAS). Subjects will also complete the The Ray Auditory Verbal Learning Test (RAVLT) to assess word memory, the Stroop test to measure attention, speed, and accuracy of thinking, and The Trail Making Test (TMT) to measure attention, speed and accuracy. A urine sample for drug screen and pregnancy test (if applicable) will also be completed. Brepiprazole capsules will be initiated at 0.5 mg/day.

Baseline 2 to Week 1: Subjects will be given the ISS to fill out at home. Subjects will be asked to complete the scale at home on 7 consecutive days between Baseline 2 and Week 1 visits and return the filled out scales to the researcher's office. The scale will take approximately 3-5 minutes to fill out.

Week 1, 2, 3, 6 (~1.5 hours each): Subjects will complete the MADRS, YMRS, IDS-SR₃₀, ISS, SAFTEE, CSSRS, AIMS, BAS, SAS, and a urine sample will be collected for a drug screen. Subjects will meet with the psychiatrist for weekly assessment and vitals will be collected.

Week 4 (~2 hours): Subjects will complete the MADRS, IDS-SR, YMRS, SAFTEE, ISS, C-SSRS, AIMS, BAS, SAS, RAVLT, Stroop, TMT, vital signs, a urine sample for a drug screen and a urine pregnancy test, and visit the doctor for a psychiatric evaluation.

Week 8 (final visit ~2.5 hours): Subjects will complete the MADRS, IDS-SR, YMRS, SAFTEE, ISS, C-SSRS, AIMS, BAS, SAS, RAVLT, Stroop, TMT, QOLBD, vital signs, a urine sample for drug screen, take a urine pregnancy test, have blood drawn for clinical testing (CBC, CMP, hs-CRP), and visit the doctor for a psychiatric evaluation and physical exam. During this visit, participants will also

be provided with aftercare referral information and will begin their medication taper. The medication taper schedule is described below under “Study Medication and Intervention Description”.

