Safety Phone Call (~15 min): Participants will receive a phone call from researchers 7-10 days following their Week 8 study visit (at the end of their tapering schedule). During this phone call, the researchers will assess any withdrawal effects or adverse events and check on the status of the aftercare referrals.

Participants will be paid for their time and inconvenience per visit as follows: \$60 at Baseline 1, Baseline 2, weeks 1, 2, 3, 6; \$70 at week 4; \$90 for week 8. Participants will also be paid for each ISS scale they bring back at the rate of \$1 per scale (maximum \$7). These payments will be processed during Week 1 visit. These payments will be completed via the ClinCard system. Bus or rail passes will be provided. After study completion, standard psychiatric care will be provided until referral is arranged.

Study Medication and Intervention Description:

Participants will be initiated on a 0.5 mg/day brexpiprazole dose (week 0/baseline); after one week the dose will be increased to 1 mg/day (week 1), after another week to 2 mg/day (week 2). If any dose appears to be poorly tolerated, the dose titration can be slowed or stopped based on clinician judgment. If response in weeks 3-6, defined as a 50% reduction in the MADRS, has not been achieved, and the current dose is well tolerated, then additional dose increases to 3 mg/day and 4 mg/day (maximum allowed dose in protocol) will occur with at least a one week interval between dose increases.

Following the last study visit (Week 8), participants will be gradually tapered off the medication every 2 days until they stop taking the medication completely. For example, if a participant takes 4 mg of brexpiprazole at Week 8, then he/she will take 3 mg for 2 days, then 2 mg for 2 days, then 1 mg for 2 days, and then 0.5 mg for 2 days. At the end of the tapering period (7-10 days depending on the highest brexpiprazole dose at the end of the study), participants will receive a safety phone call from a research staff member to assess any withdrawal symptoms and check on the status of the aftercare referrals.

5. Sub-Study Procedures:

No sub-study procedures are anticipated at this time.

6. Criteria for Inclusion of Subjects:

- Outpatient men and women ages 18-65
- Bipolar I or II disorders, currently depressed mood state based on a SCID for DSM-5; Mixed features in DSM-5 are allowed, but those with a Young Mania Rating Scale score ≥ 15 will be excluded
- MADRS score ≥ 25 at baseline 2 visit.

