All data related to the participant's participation in this study will be given a study ID which cannot be traced back to the patient except by study staff. All personal information which can identify the patient's identity will be kept separately from study documents and assessments. All clinical assessments will be collected in paper form and scores transferred to a computer database maintained on a password protected computer, on a secure server behind a firewall. The paper forms will be kept in binders marked only with the patient's study ID and will be kept in a locked room for the required time period following the completion of this study.

A Certificate of Confidentiality will be obtained for this study.

13. Potential Benefits:

This is a non-randomized open-label clinical trial, thus all participants will receive study medication. All participants may personally benefit from the study by experiencing a significant reduction in symptoms of depression associated with bipolar disorder. The researchers hope the information learned from this study will benefit others with bipolar depression in the future. Information gained from this research could lead to better treatment of patients with bipolar depression.

14. Biostatistics:

Primary Aim: Determine if brexpiprazole is associated with a reduction in depressive symptom severity in outpatients with bipolar disorder, depressed mood state.

1) The MADRS will be the primary outcome measure with the IDS-SR as a secondary outcome measure. Weekly scores on the MADRS and IDS-SR will be assessed using one-way repeated measures. Analysis of Covariance (rm-ANCOVA), controlling for age and sex as potential confounding variables, with time as the main effect. Participants will be included if they complete one post-baseline assessment (intent-to-treat sample). In addition, rates of depression response ($\geq 50\%$ reduction from baseline) and remission (≤ 10 on the MADRS and ≤ 12 on the IDS-SR) will be assessed. A significance level of 0.05 will be set for all analyses, with all tests being two-tailed.

Secondary Aims:

- 2) Assess manic symptoms in patients with bipolar disorder receiving brexpiprazole. YMRS scores will be assessed as with the primary aim above.
- 3) Assess cognition in patients with bipolar disorder receiving brexpiprazole. Scores on the RAVLT, Stroop and TMT will be assessed at baseline compared to weeks 4 and 8 separately using paired t-tests or paired-sample Wilcoxon Signed Rank test.

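### The set labelled intent-to-treat drops participants who are dosed but leave before the Week 1 rating, which can only raise the response and remission rates or leave them unchanged; the rates also name no visit

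*Combined protocol and SAP*

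**What the plan says.** The trial is single-arm: "The proposed open-label trial will examine brexpiprazole in a group of 20 bipolar depressed outpatients". Treatment begins at the Baseline 2 visit (Section 4, Study Procedures): "Brepiprazole capsules will be initiated at 0.5 mg/day". MADRS is then rated at Weeks 1, 2, 3 and 6 ("Week 1, 2, 3, 6 (~1.5 hours each): Subjects will complete the MADRS") and again at Weeks 4 and 8, which makes six post-baseline ratings. MADRS and IDS-SR are also both rated at Baseline 1 and at Baseline 2.

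Section 14, Primary Aim, describes a repeated-measures ANCOVA of the scores and then sets the sample: "Participants will be included if they complete one post-baseline assessment (intent-to-treat sample"). The next sentence adds the categorical outcomes: "In addition, rates of depression response", defined as a fall of at least 50% from baseline, and "remission (≤ 10 on the MADRS and ≤ 12 on the IDS-SR) will be assessed". It gives no visit, no rule for missing ratings and no separate denominator, and it does not say which baseline visit counts.

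The only place that ties response to a time is the dose-titration rule in Section 4, under Study Medication and Intervention Description: "If response in weeks 3-6, defined as a 50% reduction in the MADRS, has not been achieved".

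**The concern.** Intent-to-treat ordinarily signals that nobody who started treatment is left out. Here the stated rule leaves out exactly those who took the drug and left before Week 1. Their departure can be related to outcome, because Section 3 lists worsening mood that the investigators judge to require discontinuation among the reasons for stopping. In a randomised trial a similar exclusion in the control arm might partly offset this. Here nothing does.

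The second gap is the visit. With six ratings and no named time point, response could be counted at Week 8, at the last available rating, or at any visit. These give different percentages, and the choice could be made after the data are seen. In a 20-patient open-label study one participant is worth 5 points, so the percentages are sensitive to such choices.

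A smaller ambiguity sits in the remission definition, where the two cut-offs are joined by a conjunction and could be read as one joint criterion or as two separate rates.

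**Working it through.** The plan states no response rate, dropout rate, standard deviation or expected change, so there is no figure of its own to reproduce. There are two checks.

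**1. Denominator.** Input from the protocol: 20 participants. Assumed for illustration: r = 8 responders, and d participants dosed but gone before Week 1. Someone with no post-baseline rating cannot be a documented responder, so d leaves the numerator alone and only shrinks the denominator. The change is r/(20 − d) − r/20 = (r/20) × d/(20 − d), which is never negative.

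| d | Rate under the written rule | Rate in all dosed | Difference |
|---|---|---|---|
| 0 | 8/20 = 40.0% | 40.0% | 0 |
| 1 | 8/19 = 42.1% | 40.0% | 2.1 points |
| 2 | 8/18 = 44.4% | 40.0% | 4.4 points |
| 3 | 8/17 = 47.1% | 40.0% | 7.1 points |

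For scale, the exact (Clopper-Pearson) 95% interval for 8/20 is 19.1% to 63.9%.

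**2. Visit.** Without dropout, everyone who meets the criterion at Week 8 also meets it at some visit, so the any-visit rate is at least the Week 8 rate. That direction needs no assumptions. The size does, and none of the following values is in the protocol: true baseline mean 31 and SD 4, with entry at an observed score of 25 or more (the cut-off is the protocol's); Week 8 fall with mean 8 to 14 and SD 7 to 9; fractions 0.30, 0.50, 0.65, 0.75, 0.90 and 1.0 of that fall reached at Weeks 1, 2, 3, 4, 6 and 8; rating-error SD 3 to 5. Response is a fall of at least 50% from the observed baseline.

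- Errors independent across visits, mean fall 11, rating SD 4: Week 8 response 30–33%, any-visit 40–42%.
- The same with rating SD 5: 32–35% against 47–48%.
- Errors independent, all mean falls 8 to 14 and rating SD 3 to 5: gap about 4 to 16 points.
- Errors correlated 0.8 per week, mean fall 11, rating SD 4: gap about 3 to 4 points.
- Errors correlated 0.8 per week, full range: gap about 1.4 to 6.4 points.

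A second set of assumptions (mean change −10 to −17, between-person SD of change 8, visit SD 3 or 5, independent errors, no dropout) gave 6.3 to 16.4 points. Taken together, the gap is roughly 1 to 16 points.

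**Both together, one scenario.** Under the second set, take mean change −14, visit SD 5, and 20% dropout unrelated to outcome, 5% of it before Week 1:

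- Week 8, all dosed, missing counted as not met: 36.0%.
- The same, but only in those with a post-baseline rating: 37.8%. The denominator adds 37.8 − 36.0 = 1.8 points.
- Any visit, in those with a post-baseline rating: 56.3%. The total difference is 56.3 − 36.0 = 20.3 points.
- Week 8 had nobody dropped out: 44.9%. Against that, the any-visit excess is 56.3 − 44.9 = 11.4 points.

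Most of the combined difference therefore comes from the visit definition and the handling of missing ratings, and little from early leavers.

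**The case against.** The strongest reply is that the text is incomplete, not biased. Where Section 14 does fix times it uses definite ones (Weeks 4 and 8 for cognition, baseline against exit for hs-CRP), so a Week 8 rate is at least as natural a reading as any other. This stands. A reader might infer from the titration rule that response means ever achieved, but that rule governs dosing in Weeks 3 to 6 and does not define an endpoint.

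A reader might also infer that the plan permits a rate among completers only. With 8 responders, 2 early leavers and 4 later ones that would be 8/14 = 57%. The written rule excludes this: anyone with one post-baseline rating stays in, so the denominator is 18 and the rate 44.4%.

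The size of the visit gap is open to challenge, because every variability input is assumed and independent rating errors make a single low score more likely. This also stands, which is why the range reaches down to about 1 point.

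Nor is a Week 8 rate with missing counted as not met the true rate. It is a conservative convention. Against the rate had nobody dropped out, the any-visit excess under outcome-unrelated dropout ran from −0.6 to +11.4 points, so overstatement on that comparison is not certain.

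The inclusion sentence directly follows the ANCOVA sentence, so applying it to the rates is the natural reading but is not explicit. The rates are additional to the primary analysis and no decision rule hangs on them. Scale-specific remission cut-offs are the ordinary reading, and a joint criterion could only lower the remission rate.

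None of this answers the central point: a stated rule, under a label that says otherwise, removes dosed participants.

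**Conclusion.** The concern holds in a limited form. The set called intent-to-treat excludes participants dosed at Baseline 2 who leave before Week 1. If it serves as the denominator for the rates, it can only raise them or leave them unchanged: by 2.1 to 7.1 points for one to three early leavers, given 8 responders among 20 dosed. The number of early leavers and of responders is assumed; the direction is not.

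The unnamed visit is mainly missing detail. It leaves open an any-visit rate that, without dropout, cannot be below the Week 8 rate and may exceed it by roughly 1 to 16 points, depending on rating SD and on how strongly rating errors correlate across visits. The documents do not support saying that the plan will report inflated rates; they support saying that it does not rule them out. The primary MADRS ANCOVA does not depend on the missing visit.

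**What to change.** Replace the response and remission sentence in Section 14 with wording such as:

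> MADRS response, MADRS remission, IDS-SR response and IDS-SR remission are four separate rates, assessed at Week 8, with response measured against the Baseline 2 score. The denominator is every participant who received brexpiprazole. A participant without a Week 8 rating is counted as not meeting the criterion; this is a conservative convention. Each rate is given with an exact 95% confidence interval. Rates at any visit or at the last observation are descriptive only.

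In the preceding sentence, rename the set of participants with at least one post-baseline assessment the modified intent-to-treat sample.

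This is a change of wording. It needs no new data, visits or participants. The cost is that the reported rates may be slightly less favourable.
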